17.1.2. INDIVIDUAL TROUGH PARAMETERS

The following olorofim trough parameters will be calculated for each patient for the main and extended study phases based on central laboratory data. All trough concentrations, even unscheduled, will be included in these calculations, with the exceptions of the exclusions mentioned above.

Troughmax	Maximum trough concentration
Troughmin	Minimum trough concentration
Troughmed	Median trough concentration
Troughavg	Average trough concentration

These trough parameters will be listed and summarized using descriptive statistics by dosing type (Adjusted, fixed, and all combined) and study phase (main and extended), as appropriate. In addition, trough parameters will be summarized by demographics (sex, age, race) and underlying condition (immune status, baseline creatinine clearance, GvHD) for the main study phase only.

17.2. INTENSIVE PHARMACOKINETIC PARAMETERS

Subjects with partial data will be evaluated on a case by case basis to determine if they have sufficient data for PK

Document:	\\weedc-vnasc01\BIOSdata\F2G\F901318\		
Author:		Version Number:	3.0
		Version Date:	06Apr2023
Template No.:	CS_TP_BS016 Revision 6	Reference:	CS_WI_BS005
Effective Date:	02Dec2019		

F2G Ltd.
PROTOCOL F901318/0032

parameter analysis.

For PK parameter calculations, if the end of tau concentration is missing, the predose result will be substituted for the missing end of tau sample. If the predose sample is missing the end of tau concentration will be substituted for the missing predose sample). Any BLQ concentration will be assigned a value of ½ LLOQ

The following plasma PK parameters will be estimated for olorofim and [REDACTED] after intensive PK sampling on [REDACTED] by non-compartmental methods using actual elapsed time from dosing (rounded to 2 decimal places). A minimum of 3 quantifiable concentration-time data points will be required for calculation of PK parameters..

C_{max}	Maximum concentration obtained directly from the observed concentration versus time data.
C_{max}/D	Dose-normalized C_{max} ($\mu\text{g}/\text{mL}/\text{mg}$), calculated by dividing C_{max} by the dose of olorofim.
T_{max}	Time of maximum concentration, obtained directly from the observed concentration versus time data.
C_{min}	Minimum concentration after multiple dosing, obtained directly from the observed concentration versus time data.
C_{min}/D	Dose-normalized C_{min} ($\mu\text{g}/\text{mL}/\text{mg}$), calculated by dividing C_{min} by the dose of olorofim.
$C_{(0)}$	Predose concentration on intensive PK day
$C_{(0)}/C_{min}$	Ratio of $C_{(0)}/C_{min}$
T_{min}	Time of minimum concentration after multiple dosing, obtained directly from the observed concentration versus time data.
C_{avg}	Average concentration over the dosing interval tau, calculated as $AUC_{(0-\tau)}$ divided by the dosing interval, tau. Actual elapsed time at the end of the dosing interval will be used for the calculation.
C_{avg}/D	Dose-normalized C_{avg} ($\mu\text{g}/\text{mL}/\text{mg}$), calculated by dividing C_{avg} by the dose of olorofim.
$AUC_{0-\tau}$	Area under the concentration-time curve during a dosing interval "tau". Actual elapsed time at the end of the dosing interval will be used for the calculation. If actual time is not within 80% to 120% of the dosing interval, or if more than 25% of scheduled sampling occasions over the dosing interval are missing, $AUC_{(0-\tau)}$ will not be reported.
$AUC_{0-\tau}/D$	Dose-normalized $AUC_{0-\tau}$ ($\mu\text{g}\cdot\text{h}/\text{mL}/\text{mg}$), calculated by dividing $AUC_{0-\tau}$ by the

Document: \\weedc-vnasc01\BIOSdata\F2G\F901318 [REDACTED]
Author: [REDACTED] Version Number: 3.0
Version Date: 06Apr2023
Template No.: CS_TP_BS016 Revision 6 Reference: CS_WI_BS005
Effective Date: 02Dec2019

F2G Ltd.
PROTOCOL F901318/0032

	dose of orlofim.
AUC ₀₋₂₄	AUC _{0-tau} multiplied by a factor of 2 and 3 for BID and TID dosing, respectively.
AUC ₀₋₂₄ /D	Dose-normalized AUC ₀₋₂₄ (µg*h/mL/mg), calculated by dividing AUC ₀₋₂₄ by the dose of orlofim.
CL/F	Apparent systemic clearance after extravascular dosing, calculated as dose divided by AUC _{0-tau} . Calculated for orlofim only.
MRC _{max}	Ratio of metabolite [REDACTED] C _{max} to parent orlofim C _{max} , and adjusted for the ratio of molecular weights (498/514).
MRAUC _{0-tau}	Ratio of metabolite [REDACTED] AUC _{0-tau} to parent orlofim AUC _{0-tau} , and adjusted for the ratio of molecular weights (498/514).

Area under the concentration-time curve will be calculated by linear up/log down trapezoidal summation. No dose adjustment is necessary for the calculation of the selected parameters. Pharmacokinetic parameters will be summarized using descriptive statistics for each analyte and dosing type (adjusted, fixed and combined). Summaries of orlofim PK parameters by demographics (sex, age, race) and underlying condition (immune status, baseline creatinine clearance, GvHD) will also be produced. A subject listing of individual PK parameters will be provided. Box/Whisker plots of individual intensive PK day C_{max}, C_{min}, and AUC_{0-tau}, presented by analyte and dosing type, will be provided, together with mean and 95% confidence intervals for selected orlofim PK parameters presented by demographics and underlying condition.

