15.1. DERIVATIONS

Overall compliance to main study medication—based on the drug accountability and exposure data—will be calculated as the actual number of tablets taken (prescribed number of tablets as recorded on exposure eCRF – total number of missed tablets) divided by the prescribed number of tablets expressed as a percentage.

Up to and including protocol amendment 4 patients will receive a loading regimen of approximately 4 mg/kg of F901318 divided into two or three doses (12 or 8 hours apart respectively), followed by a maintenance regimen of approximately 2.5 mg/kg/day divided into two or three doses from Day 2 onwards. Based upon emerging data from studies in healthy volunteers, the recommended dose regimen may be revised to total daily dosages of up to 300 mg

Document: \\weedc-vnasc01\BIOSdata\F2G\F901318\ [Redacted]
Author: [Redacted] Version Number: 3.0
Version Date: 06Apr2023
Template No.: CS_TP_BS016 Revision 6 Reference: CS_WI_BS005
Effective Date: 02Dec2019

divided into two or three doses.

From protocol amendment 6 onwards patients will receive a one-day oral loading dose of 150 mg bid (dosed 12 ± 1 hours apart) followed by a maintenance dose regimen of 90 mg bid (dosed 12 ± 1 hours apart) from Day 2 onwards. Based upon clinical evaluation of efficacy by the Investigator, stepwise increases of maintenance doses of F901318 (to 120 mg bid, then 150 mg bid) may be permitted, following discussion with the MM.

Due to the dose changing nature of this study, prescribed number of tablets will be calculated from the Exposure eCRF page as follows:

$[(\text{Dose number 1's End date and time of study medication administration} - \text{Dose number 1's Start date and time of study medication administration} + 1) \times \text{Dose number 1's Total Daily Dose}] + [(\text{Dose number 2's End date and time of study medication administration} - \text{Dose number 2's Start date and time of study medication administration} + 1) \times \text{Dose number 2's Total Daily Dose}]$

+ ... +

$[(\text{Dose number n's End date and time of study medication administration} - \text{Dose number n's Start date and time of study medication administration} + 1) \times \text{Dose number n's Total Daily Dose}]$,

where n is the largest dose number recorded on the Exposure eCRF page with End date of study medication administration equal to the date of last study medication for the main study phase. <<divide by 30 (30mg per tablet)>>

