17. PHARMACOKINETIC ANALYSIS

[figure not shown]
The PK parameter calculations will be the responsibility of the clinical pharmacokineticist at IQVIA, Overland Park, Kansas, United States. The concentration summaries, PK parameter summaries, data listings, and associated graphic presentation will be the responsibility of the study biostatistician at IQVIA, Bloemfontein, South Africa.

Scheduled intensive PK day plasma concentrations and PK parameters for olorofim (central bioanalytical lab) will be summarized using descriptive statistics, including n, mean, SD, coefficient of variation (CV%), median, minimum, and maximum. geometric mean, and CV% for geometric mean (GeoCV%). For time of maximum concentration (Tmax), only n, median, minimum, and maximum will be provided. If the number of non-missing observations at a time point is fewer than 3, the data at the time point will not be summarized. Scheduled intensive PK day plasma concentrations and PK parameters will be summarised by dosing methodology (adjusted (all), adjusted (BID), adjusted (TID) or fixed dosing) using descriptive statistics, including n, mean, median, 95% CI, minimum and maximum. Intensive PK day PK parameters will also be summarised by concomitant medication (CYP3A4 inhibitors and inducers) demographics (age, sex, race) and underlying condition (immune status, baseline creatinine clearance, GvHD) using descriptive statistics, including n, mean, median, 95% CI, minimum, and maximum.

In general, scheduled trough data (central bioanalytical lab and regional hub) will be summarised by dosing methodology (adjusted or fixed dosing) and regimen (BID or TID) using descriptive statistics, including including , mean, SD, coefficient of variation (CV%), median, minimum, and maximum, geometric mean, and CV% for geometric mean (GeoCV%). Trough parameters will be summarised by dosing methodology (adjusted (all), adjusted (BID), adjusted (TID) or fixed dosing), concomitant medication (CYP3A4 inhibitors and inducers), demographics (age, sex, race) and underlying condition (immune status, baseline creatinine clearance, GvHD) using descriptive statistics, including n, mean, median, 95% CI, minimum, and maximum.

Document: \\weedc-vnasc01\BIOSdata\F2G\F901318 [REDACTED]
Author: [REDACTED] Version Number: 3.0
Version Date: 06Apr2023
Template No.: CS_TP_BS016 Revision 6 Reference: CS_WI_BS005
Effective Date: 02Dec2019

F2G Ltd.
PROTOCOL F901318/0032

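### SAP 17.2 gives dose-normalised AUC0-24 no daily-dose divisor: read consistently with CL/F, it comes out 1.5 times higher for TID than for BID patients with the same clearance

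*SAP*

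**What the plan says.** The parameter table in SAP 17.2 defines AUC0-24 as AUC0-tau "multiplied by a factor of 2 and 3 for BID and TID dosing, respectively". The next row, AUC0-24/D, divides that "by the dose of orlofim" (the SAP's spelling of olorofim there). The other normalised parameters (Cmax/D, Cmin/D, Cavg/D and AUC0-tau/D) also divide by the dose of the drug, without saying whether this is one administration or a day's total. CL/F is "calculated as dose divided by" AUC0-tau. Below the table the SAP adds: "No dose adjustment is necessary for the calculation of the selected parameters". SAP 17.2 names no daily dose. SAP 15.1, on compliance, does: it works from "Dose number 1's Total Daily Dose" on the Exposure eCRF page.

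Both schedules are expected in the data. SAP 3.1 says that patients treated up to and including Amendment 4 took their daily amount in two doses 12 hours apart or three doses 8 hours apart. The fixed regimen from Amendment 6 is BID only.

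On presentation, SAP 17.2 says: "Pharmacokinetic parameters will be summarized using descriptive statistics for each analyte and dosing type (adjusted, fixed and combined". It also plans olorofim summaries by demographics and underlying condition, with no split by schedule. SAP 17 plans intensive-day parameters "summarised by dosing methodology (adjusted (all), adjusted (BID), adjusted (TID) or fixed dosing". SAP 17.1.1 adds co-medication summaries of selected parameters.

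**The concern.** A dose-normalised exposure is meant to be comparable between patients on different doses. That requires numerator and divisor to cover the same period. Here the numerator covers a day, while the divisor, taken in the sense that CL/F needs, covers one dosing interval. Two patients with the same clearance and the same daily amount would then show different values only because one splits the day into three doses and the other into two.

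At stake is the reading of the descriptive PK tables. The adjusted group mixes BID and TID while the fixed group does not, so a contrast between them would carry a frequency component. A demographic or underlying-condition subgroup with a larger TID share would appear to have higher exposure per mg. The effect of co-medication on PK is a listed protocol endpoint, and its tables could be affected in the same way.

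**Working it through.** **Inputs**
- Scaling factors 2 and 3, and CL/F as dose over AUC0-tau: SAP 17.2.
- Intervals of 12 h (BID) and 8 h (TID): SAP 3.1.
- Share of TID patients, p: not given in the documents; assumed 10% to 50%.
- Numerical check only (assumed): CL/F 5 L/h, absorption rate 1 per h, 180 mg a day split in two or three, and a half-life of 27 h, inside the 24 to 30 h of protocol 4.2.

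**1. The SAP's factors.** 24/12 = 2 and 24/8 = 3. They reproduce.

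**2. AUC0-24/D with the single dose d.** Rearranging the SAP's own CL/F gives AUC0-tau = d/(CL/F) at steady state under linear kinetics.
- BID: 2 × [d/(CL/F)] / d = 2/(CL/F)
- TID: 3 × [d/(CL/F)] / d = 3/(CL/F)
- TID:BID = 3/2 = 1.50 at any dose level.

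**3. Cavg/D with the single dose.** Cavg = AUC0-tau/tau.
- BID: 1/(12 CL/F)
- TID: 1/(8 CL/F)
- TID:BID = 12/8 = 1.50.

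**4. Can another meaning of dose rescue the table?** Put the total daily dose (2d or 3d) everywhere.
- AUC0-24/D becomes 1/(CL/F) for both schedules, ratio 1.00.
- CL/F becomes 2 times (BID) or 3 times (TID) its true value.
- AUC0-tau/D falls to 1/2 (BID) or 1/3 (TID) of its single-dose value.

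No single meaning makes every row comparable across schedules.

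**5. Numerical check.** A one-compartment oral steady-state model with linear-up/log-down AUC:

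| | 90 mg BID | 60 mg TID | TID:BID |
|---|---|---|---|
| AUC0-24 (µg·h/mL) | 36.0 | 36.0 | 1.00 |
| AUC0-24 / single dose (µg·h/mL/mg) | 0.400 | 0.600 | 1.50 |
| AUC0-24 / total daily dose (µg·h/mL/mg) | 0.200 | 0.200 | 1.00 |

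These doses are for illustration only.

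**6. Effect on a pooled mean.** With equal clearance, the mean relative to an all-BID group is (1 − p) + 1.5p = 1 + 0.5p.
- p = 10%: 1.05
- p = 30%: 1.15
- p = 50%: 1.25

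Two subgroups with assumed TID shares of 50% and 10% would differ by 1.25/1.05 = 1.19 with no difference in clearance.

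**7. Interval length (separate and smaller).** AUC0-tau runs to the actual end of the interval and is withheld "If actual time is not within 80% to 120% of the dosing interval", but the multiplier stays at exactly 2 or 3. At the limits the 24-hour value covers 2 × 9.6 = 19.2 h to 2 × 14.4 = 28.8 h (TID: 3 × 6.4 and 3 × 9.6, the same range).

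**The case against.** **The SAP never says single dose.** For a 24-hour AUC the daily total is a natural divisor, and the field exists. This stands as far as intent goes: a programmer might choose correctly. But the same undefined word serves the whole table, CL/F fixes its meaning as the single dose, and nothing tells the programmer to switch for one row.

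**Valid measures are already planned.** AUC0-tau/D by the single dose and CL/F do not depend on frequency, and AUC0-tau/D equals the corrected AUC0-24/D. Separate adjusted (BID) and adjusted (TID) summaries are also planned. This stands and limits the damage. The pooled tables remain, however, and the separate columns would still differ by 1.5 for no pharmacokinetic reason.

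**Cmax/D and Cmin/D per administered dose are not errors.** This stands. More frequent dosing really does raise steady-state concentration per administered mg. In a one-compartment model with half-life 24 or 30 h and assumed absorption rates of 0.5 or 1.0 per h, TID:BID is about 1.43 to 1.46 for Cmax/D and 1.57 to 1.59 for Cmin/D. The same defence covers Cavg/D in part: it is a legitimate per-dose quantity, but it should not be pooled across schedules.

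**The reach is uncertain.** The TID share is unknown, and a subgroup contrast is distorted only if that share differs between groups. SAP 17.1.1 covers selected parameters, so co-medication tables are affected only if these are chosen. The box plots specified in SAP 17.2 use no normalised parameter.

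**A stronger reading to avoid.** A reader might infer that this flaw undermines the adjusted-versus-fixed comparison behind the Amendment 06 dosing change. The documents do not support that. The protocol's summary of changes attributes the removal of weight-based dosing to population PK modelling. The amendment is dated February 2020, whereas this SAP version is from 2023. Nothing links AUC0-24/D or Cavg/D to the decision.

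**Conclusion.** The point holds for AUC0-24/D, and for Cavg/D wherever schedules are pooled or compared. With dose read as CL/F requires, both are exactly 1.50 times higher for TID at equal clearance, assuming linear steady-state kinetics. The alternative reading moves the error to CL/F, so the definitions need changing whichever was meant.

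The summaries exposed are adjusted (all), adjusted, combined, adjusted beside fixed, demographic and underlying-condition tables, and co-medication tables if these parameters are selected. The size in a pooled mean depends wholly on the TID share, so the range of 5% to 25% is an assumption and not an estimate.

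The interval-length issue is secondary. The 80% to 120% limits are acceptance bounds, and the actual deviations are unknown.

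This is a correction to make before the PK tables are produced, and it does not threaten the trial's conclusions. It concerns a calculation rule only and says nothing about which schedule or dose is appropriate.

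**What to change.** In SAP 17.2:

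1. Define AUC0-24/D as AUC0-24 divided by the total daily dose in force on the intensive PK day.
2. State that D is the single administered dose for Cmax/D, Cmin/D, AUC0-tau/D and CL/F.
3. Either divide Cavg by the total daily dose, or show Cavg/D by regimen. Show Cmax/D and Cmin/D by regimen rather than pooled.
4. Optionally, compute AUC0-24 as Cavg × 24. Cavg already uses the actual interval length, so accepted deviations would no longer be scaled into the 24-hour value.

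The cost is a few lines of SAP text and matching program changes. The total daily dose is already on the Exposure eCRF, so no new data are needed.

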8.11.2 Intensive PK Data Analysis

The Intensive PK study will include densely sampled PK to allow parameters to be determined using standard noncompartmental analysis. All PK parameters where possible to estimate will be listed and summarised using appropriate descriptive statistics including maximum plasma concentration (C_{max}), time to maximum plasma concentration (t_{max}), area under the curve over the 12 hour dosing interval (AUC_{tau}), trough concentration 12 hours post-dose (C_{min}), apparent clearance (CL/F) and apparent volume of distribution (V_z/F). Data will be listed and summarised using n, arithmetic mean, standard deviation, coefficient of variation, median, minimum and maximum values. Geometric mean and geometric coefficient of variation will also be included for any PK parameter calculations, except for t_{max} which will be summarised using n, minimum, median and maximum only. Full details of the analysis will be provided in the SAP supporting this clinical study.

8.12

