The study has two phases: the main study phase (Figure A) and the extended treatment phase (Figure B).

Up to and including protocol amendment 4 patients will receive a loading regimen of approximately 4 mg/kg of F901318 divided into two or three doses (12 or 8 hours apart respectively), followed by a maintenance regimen of approximately 2.5 mg/kg/day divided into two or three doses from Day 2 onwards. Based upon emerging data from studies in healthy volunteers, the recommended dose regimen may be revised to total daily dosages of up to 300 mg divided into two or three doses.

From protocol amendment 6 onwards patients will receive a one-day oral loading dose of 150 mg bid (dosed 12 ± 1 hours apart) followed by a maintenance dose regimen of 90 mg bid (dosed 12 ± 1 hours apart) from Day 2 onwards. Based upon clinical evaluation of efficacy by the Investigator, stepwise increases of maintenance doses of F901318 (to 120 mg bid, then 150 mg bid) may be permitted, following discussion with the MM.

Document: \\ieedc-vnasc01\BIOSdata\F2G\F901318\ [Redacted]
Author: [Redacted] Version Number: 3.0
Version Date: 06Apr2023
Template No.: CS_TP_BS016 Revision 6 Reference: CS_WI_BS005
Effective Date: 02Dec2019

[figure not shown]

F2G Ltd.
PROTOCOL F901318/0032

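### AUC0-tau is an 8 h area for TID patients and a 12 h area for BID patients, yet it is pooled across regimens, so pooled AUC0-tau shifts with regimen mix alone

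*SAP*

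**What the plan says.** SAP 3.1 describes two dosing eras. Up to Amendment 4 the weight-adjusted loading regimen was "divided into two or three doses (12 or 8 hours apart respectively"). Maintenance in that era was likewise a daily amount that could be split either way: "maintenance regimen of approximately 2.5 mg/kg/day divided into two or three doses from Day 2 onwards". From Amendment 6 it is a fixed "maintenance dose regimen of 90 mg bid (dosed 12 ± 1 hours apart) from Day 2 onwards". Adjusted-dose patients can therefore have a 12 h or an 8 h interval, while fixed-dose patients have only a 12 h interval.

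SAP 17.2 defines AUC0-tau as "Area under the concentration-time curve during a dosing interval", with no scaling to a common time. The same list contains two measures that are scaled. AUC0-24 is AUC0-tau "multiplied by a factor of 2 and 3 for BID and TID dosing, respectively". Cavg is the "Average concentration over the dosing interval tau, calculated as" AUC0-tau over tau.

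The displays are as follows:

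- SAP 17 summarises intensive PK parameters in four columns: adjusted (all), adjusted (BID), adjusted (TID) and fixed. It also summarises them by co-medication, demographics and underlying condition, with no regimen split stated.
- SAP 17.2 uses three columns: "Pharmacokinetic parameters will be summarized using descriptive statistics for each analyte and dosing type (adjusted, fixed and combined"). It repeats the demographic and underlying-condition summaries, and names Cmax, Cmin and AUC0-tau for the box plots by dosing type.
- SAP 17.1 sets the box-plot panels for intensive PK parameters as adjusted, fixed and combined.
- The co-medication group summary in SAP 17.1.1, and the mean and confidence-interval figures in 17.1, 17.1.1 and 17.2, cover selected parameters. Which ones are selected is not said.

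Protocol 8.11.2 describes AUCtau only as the "area under the curve over the 12 hour dosing interval".

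**The concern.** An area under the curve can be compared between patients only if it covers the same number of hours. A TID patient and a BID patient with the same daily dose and the same clearance have the same average concentration all day. The TID patient nevertheless contributes a smaller AUC0-tau, because the area stops at 8 h.

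When the two are averaged, the pooled figure depends on how many patients were on TID. Fixed dosing is BID only, so an adjusted box that contains TID patients sits lower than the fixed box for a reason unrelated to exposure. Two subgroups with different TID shares would differ in the same way. No note is planned to tell the reader of a pooled box plot or subgroup table that the areas span different hours.

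At stake is the reading of descriptive PK displays. No test, decision rule or efficacy result depends on them.

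**Working it through.** **Inputs from the documents.** Interval 12 h (BID) or 8 h (TID), a daily maintenance amount split two or three ways, and fixed dosing of 90 mg BID, or 180 mg/day (all SAP 3.1). Scaling factors of 2 and 3 (SAP 17.2). Terminal half-life 24 to 30 h (Protocol 4.2).

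**Assumptions.** Linear PK at steady state, equal daily dose and equal CL/F across regimens, and a TID share f, which the documents do not give.

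**Step 1: reproduce the SAP's factors.** 24/12 = 2 for BID and 24/8 = 3 for TID. Both agree with SAP 17.2.

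**Step 2: AUC0-tau by regimen.** At steady state AUC0-tau = (dose per interval)/(CL/F). With 180 mg/day and CL/F = 1:

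- BID: 180/2 = 90
- TID: 180/3 = 60
- Ratio TID/BID: 60/90 = 0.667

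Numerical integration of a one-compartment oral model (half-life 24 and 30 h, absorption rate constant assumed to be 1 per hour) gave the same 90 and 60.

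**Step 3: pooled AUC0-tau relative to an all-BID group.** The arithmetic mean is (1 − f) + f × 2/3 = 1 − f/3. The geometric mean is (2/3)^f.

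| TID share f (assumed) | Arithmetic mean ratio | Shortfall | Geometric mean ratio |
|---|---|---|---|
| 10% | 0.967 | 3.3% | 0.960 |
| 25% | 0.917 | 8.3% | 0.904 |
| 50% | 0.833 | 16.7% | 0.816 |
| 75% | 0.750 | 25.0% | 0.738 |
| 100% | 0.667 | 33.3% | 0.667 |

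**Step 4: other pooled displays.**

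- Combined column with a share g on adjusted dosing: 1 − g × f/3. At g = f = 50% this is 0.917, a shortfall of 8.3%.
- Two subgroups with TID shares of 75% and 25%: 0.750/0.917 = 0.82, with no true difference.

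**Step 5: the scaled measures.**

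- AUC0-24: 90 × 2 = 180 and 60 × 3 = 180
- Cavg: 90/12 = 7.5 and 60/8 = 7.5
- CL/F: 90/90 = 1 and 60/60 = 1

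None of these depends on regimen.

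**Step 6: why the replacement should be un-normalised.** SAP 17.2 does not say whether the dose in AUC0-24/D is the single or the daily dose. With the single dose it is 180/90 = 2 for BID and 180/60 = 3 for TID, so the regimen effect returns as a factor of 1.5 in the other direction.

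**The case against.** The strongest reply is that the plan already contains most of the remedy. SAP 17 provides adjusted (BID) and adjusted (TID) columns, so adjusted BID can be compared with fixed BID on equal terms. AUC0-24, Cavg and CL/F belong to the same parameter set, and the sentence governing the pooled summaries is not limited to AUC0-tau. On its plain wording those tables carry the scaled measures alongside it. This stands. It reduces the problem to the AUC0-tau rows in pooled tables and to the box plots, where only AUC0-tau is named.

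The size is also hypothetical. The TID share is unknown, and equal daily dose is not guaranteed: 180 mg/day matches 2.5 mg/kg/day only at 180/2.5 = 72 kg. Nothing in the documents suggests that TID use differs by sex, race, GvHD or co-medication. This stands too, and is why a range is shown.

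The protocol's 12 h definition is not an error. It fits the current twice-daily regimen, and the SAP uses a general interval because it also covers patients dosed earlier.

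Three stronger readings are tempting and not supported:

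- A reader might infer that pooled exposure in general is understated. Only AUC0-tau shifts.
- A reader might infer that the artefact bears on the Amendment 6 dose change. That amendment is dated 28 February 2020 and gives population PK modelling as the basis for removing weight adjustment. The SAP version in hand is dated 6 April 2023, and these tables are not the stated basis.
- A reader might infer that the covariate conclusions are at risk. The protocol assigns covariate effects to nonlinear mixed-effects modelling under a separate plan.

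**Conclusion.** The point holds as a minor correction to descriptive secondary PK. AUC0-tau is pooled over 8 h and 12 h intervals in the adjusted, adjusted (all) and combined columns, in the demographic, underlying-condition and general co-medication summaries, and in the box plots by dosing type. At equal daily dose and clearance under linear steady-state PK, the pooled mean falls by f/3 relative to BID: 8%, 17% or 25% at assumed TID shares of 25%, 50% or 75%, and at most one third. If no patient in a pooled group was on TID, there is no effect.

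Whether AUC0-tau appears in the SAP 17.1.1 co-medication group summary or in the mean and confidence-interval figures cannot be determined, because the selected parameters are not named. The primary efficacy analysis is untouched.

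**What to change.** In SAP 17, 17.1, 17.1.1 and 17.2:

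1. In the box plots by dosing type, replace AUC0-tau with un-normalised AUC0-24 (or Cavg).
2. Use AUC0-24 (or Cavg) as the AUC measure in every summary that pools BID and TID patients: adjusted, adjusted (all), combined, demographic, underlying condition and co-medication.
3. Show AUC0-tau only in the fixed, adjusted (BID) and adjusted (TID) columns, and use the same columns in 17.2 as in 17.
4. Name the selected parameters in 17.1, 17.1.1 and 17.2, and apply the same rule to them.
5. State whether the dose in AUC0-24/D is the single or the daily dose.

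The cost is a few lines of SAP text and a variable swap in the affected tables and plots. AUC0-24 and Cavg are already derived, so no new data or calculations are needed.
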